	17.1 Case Report Forms17.2 Laboratory Accreditation and Normal Values		
	17.2 Laboratory Accreditation and Norman Values 17.3 Data Review		
	17.4 Data Ownership and Sharing Plan		
18.0	Maintenance of Study Documentation		
19.0	Record Retention 4		
20.0	Study Oversight	40	

Appendix A:	Time and Event Schedule	42
Appendix B:	INTERMACS [®] Patient Profiles	43
Appendix C:	New York Heart Association (NYHA) Functional Classification	45
Appendix D:	Study Specific Reportable Events/Outcomes	46

Study Summary

REVIVE-IT REGI	REVIVE-IT REGISTRY (REVIVAL)					
Name of Funding Sponsor:						
National Heart, Lung, and Blood Institute						
Title of Protocol:						
REVIVAL: Registry Evaluation of Vital Information for VADS in Ambulatory Life						
Study Number:						
NHLBI Solicitation Number: RFP NHLBI-HV-10-14 NHLBI Contract Number: HHSN268201100026C						
Study Design:						
The REVIVE-IT Registry (i.e., REVIVAL) is a prospective cohort study to be conducted in up to twenty five (25) participating Clinical Sites in the USA. The study will continue until up to 400 eligible heart failure heart failure subjects have been enrolled (estimated length of accrual is 12 months).						
Objectives:						
 To characterize clinical outcomes, quality of life and functional impairment over two (2) years in a population of ambulatory patients on evidence-based therapy with advanced chronic systolic heart failure who may benefit from VAD therapy To evaluate the relationship between heart failure subject's modeled prognosis, self assessed prognosis, preferences for end of life care and thresholds for considering VAD implant To evaluate caregiver burden associated with heart failure subject's measures of heart failure severity, quality of life, functional limitations and with preferences for care and thresholds for considering device implant To determine health-associated costs for heart failure subjects in the registry To provide the REVIVE-IT Registry to the INTERMACS study group to be used in comparative analyses of outcomes of patients treated with medical versus VAD therapy 						
Number of Subjects: Number of Sites:						
Up to 400 patients will be consented into the Registry.	Up to 25 Clinical Sites in the US					
Period of Evaluation: Patients will be followed for up to 2 years post-enroll	ment					
Major Criteria for Evaluation and Analyses:						
1. Hospitalizations						
 Stroke Mechanical Circulatory Support Device (MCS) 	SD)*					
4. Transplant*	,					
5. Death (Cardiovascular related vs. Non-cardio	ovascular related)*					
* Outcomes of death, transplant and implants of a durable VAD will be considered study endpoints with no additional follow-up in REVIVAL. When a study endpoint has been reached, events/outcomes up through the point of the outcome will be reported on the eCRFs.						
Main Criteria for Inclusion:						
 Ambulatory. Chronic systolic heart failure ≥ 12 months. 						
 Offoric system rear failure 2 12 months. NYHA II - IV for at least 45 of the last 60 days. 						
 Last documented left ventricular ejection fraction ≤ 35% by any imaging modality. 						
 Age 18 - 80 years. Under the care of a cardiologist at the study site. 						
 On appropriate evidenced-based heart failure medications – ACE inhibitor, ARB or 						

sacubitril/valsartan [LCZ-696]; beta blocker; aldosterone antagonist; hydralazine/long-acting nitrate [required of African-American subjects only] for \geq 3 months absent contraindications or intolerances. 8. Has ICD or CRT-D. If CRT-D, present for \geq 3 months. 9. Demonstrated advanced heart failure, including any one of the following*: Serum sodium ≤ 135 mEq/L (obtained as an outpatient)** i. Serum BNP \geq 750 pg/mL or NT-proBNP \geq 3000 pg/mL^{**} (obtained as an ii. outpatient) Seattle Heart Failure Model (SHFM) one year predicted survival ≤ 85%** iii. Heart Failure Survival Score (HFSS) ≤ 7.19** iv. Peak VO₂ \leq 55% of predicted for age by Wasserman equation or \leq 14 ml/kg/min, ٧. with RER ≥ 1.05*** VE/VC02 slope > 40*** vi. 6 minute walk test (6MWT) distance \leq 350 m without significant non-cardiac vii. limitation** viii. Currently listed as Heart Transplant Status II due to heart failure limitation Or History of one (1) hospitalization (\geq 24 hours) for acute or acute on chronic heart failure in the past year with additional history to include: Serum BNP \geq 500 pg/mL or NT-proBNP \geq 2000 pg/mL^{**} (obtained as an i. outpatient) Or History of two (2) hospitalizations (≥ 24 hours) for acute or acute on chronic heart failure in the past year. * Qualifying measure must be the most recent of that type of measure obtained (i.e., a BNP \geq 1000 obtained 2 months prior would not qualify the heart failure subject if a more recent BNP was < 1000) **Using values obtained within the prior 90 days, except for peak VO2 within 365 days ***Obtained within the prior 365 days 10. Willingness to continue to receive heart failure care from the enrolling advanced heart failure clinic over the next two (2) years and to come for all scheduled study visits. 11. Written Informed consent given. Main Criteria for Exclusion: 1. Known serious medical problem other than heart failure that would be expected to limit 2-year survival (≥50% mortality within 2 years from non-heart failure diagnosis). 2. Patient is not likely to be compliant with the protocol, in the opinion of the Investigator. 3. Currently hospitalized. 4. Current use of an intravenous inotrope. 5. Primary functional limitation from non-cardiac diagnosis even if not likely to limit survival. 6. Chronic hemodialysis or peritoneal dialysis or a serum creatinine value of \geq 3 mg/dL at time of enrollment. 7. Cardiac amyloidosis, cardiac sarcoidosis, constrictive pericardial disease, active myocarditis or congenital heart disease with significant structural abnormality. Hypertrophic cardiomyopathy unless dilated LV and no outflow gradient. 9. Cardiac conditions that are amenable to surgical or percutaneous procedures (other than VAD or transplant) that would substantially improve prognosis and for which this subject is a reasonable candidate, regardless of whether the procedure will or will not be performed.

- 10. Uncorrected hyperthyroidism or hypothyroidism.
- 11. Pregnancy.

Statistical Considerations:

Because this registry is observational in nature, analyses will be on-going for descriptive variables. More specific analyses for hypothesis generation will be determined as appropriate.

1.0 Introduction

1.1 Rationale

Despite widespread use of evidence-based medical therapies, including neurohormonal blockers and biventricular pacing, mortality and morbidity from systolic heart failure remains high.^[1] Breakthroughs in mechanical circulatory support (MCS) technology have extended survival and improved quality of life in the most advanced heart failure patients awaiting cardiac transplantation and in inotrope-dependent patients who are ineligible for transplant.^[2-4] Left ventricular assist device (LVAD) therapy offers the promise of relieving heart failure symptoms in patients with less advanced stages of heart failure but comes with its own significant adverse effect burden. Future expansion of the target population for VAD therapy into ambulatory patients with less advanced heart failure requires improved prognostic tools to allow identification of those patients at greatest risk of dying without MCS and those who are most likely to have a favorable outcome with VAD therapy. Analyses of VAD clinical trial databases and of the INTERMACS Registry have greatly enhanced our knowledge of the latter question. The REVIVE-IT Registry (also referred to as REVIVAL to differentiate the stand-alone registry from the originally designed REVIVE-IT study where the registry was coupled to the trial) will address the former.

REVIVAL will establish a **prospective**, **observational**, **multicenter patient cohort** in ambulatory patients with chronic, advanced, systolic heart failure that will provide a greater understanding of their clinical trajectory (rates of hospitalizations, transplantation, MCSD use and death), and of how baseline clinical risk measures are related to prognosis. Within the broader goal of 1) improving prognostic assessment in chronic, ambulatory, advanced systolic heart failure, additional targeted goals are to 2) better inform the selection of appropriate candidates for a future study of a strategy of early LVAD therapy vs. optimal medical management in this population, and 3) determine the feasibility of identifying candidates for such a trial. Therefore, the target population will have known high-risk features for increased mortality and hospitalization (e.g., frequent hospitalization, reduced exercise capacity, elevated BNP or N-terminal proBNP, increased Seattle Heart Failure Model risk score, reduced Heart Failure Survival Score).

Present prognostic models have been limited by both the quality of the prognostic data and the narrowness of the outcome data (e.g., survival outcome only). The prognostic value of registry data is often limited by the restricted scope of the prognostic variables collected, poor measurement quality and missing data. Prognostic models are generally limited to predicting death or hospitalization (or both) rather than more comprehensive measures like quality adjusted life years (QALYs). REVIVAL will address this knowledge gap by creating a repository of high quality prognostic and outcome data on a cohort of patients with advanced heart failure (INTERMACS Profiles 5-7).

1.2 Background

1.2.1 Mechanical Support in Ambulatory Advanced Heart Failure

As MCS survival has increased to over 75% at one year, ambulatory patients with advanced heart failure at home on oral therapy are now being considered more often for MCS. [Figure 1] These patients with INTERMACS Profiles 4-7 still account for fewer than 20% of the over 14,000 MCS patients registered in INTERMACS (Interagency Registry of Mechanically Assisted Circulatory Support).^[5] Yet in patients receiving oral heart failure therapy in Profile 4 (persistent resting symptoms at home on oral medical therapy) the contemporary event rate exceeds 50% at one year among the population screened at 11 MCS centers for feasibility of the proposed project.^[6] In the screening pilot for the Medical Arm of Mechanically Assisted Circulatory Support (MedaMACS), INTERMACS profiling was shown to provide a powerful shorthand for describing ambulatory patients with heart failure at risk of death or progressive disease requiring advanced

cardiac therapies, with higher patient profiles denoting lower overall risk. The largest potential public health benefit from MCS is projected to be in ambulatory patients in INTERMACS Profiles 5-7 in whom MCS can be employed electively for long-term benefit with complication lower rates and improved cost-effectiveness. For this "less sick" population in whom death is not imminent, shared decision-making about MCS requires more measured and consideration individualized of risks and benefits beyond survival.^[7]

1.2.2. Risk Profiling in Ambulatory Advanced Heart Failure

Identification of patients at high risk of mortality is vital for triage to advanced cardiac therapies. The only randomized trial directly comparing MCS to medical therapy was REMATCH, which followed only 61 patients on medical therapy, many on two inotropic agents^[8] The REMATCH subgroup on oral medical therapy was only 16 patients.^[9] Classic scores such as the Heart Failure Survival Score from pre-transplant populations pre-date the advances of implantable defibrillators and resynchronization pacing.^[10] None of the other risk scores in current use are derived from or for the advanced heart failure population in whom MCS is being considered. Data from pharmacologic trials focuses on younger patients generally with mild-moderate heart failure without recent decompensation. As a result, the prevalent Seattle Heart Failure Score amalgamated from multiple clinical trials has generally underestimated mortality in advanced heart failure.^[11-13] Other risk scores derived from community populations with mean age in the mid-70s include major contributions from co-morbidities and non-cardiac mortality to overall

risk.^[14] We remain limited in our ability to identify ambulatory patients who are both sick enough and well enough to derive more benefit from MCS than from contemporary medical therapy, which itself is progressing rapidly with new therapies.^[15]

1.2.3 Ambulatory Patients Awaiting Heart Transplantation

The current allocation system in the United Network for Organ Sharing (UNOS) for heart transplantation prioritizes patients according to level of illness and allows listing of ambulatory patients who do not require intravenous therapies or mechanical support in UNOS Status 2. Improving survival on the waiting list, in part because of more widespread bridging with MCS, has led to increasing waiting times until transplant.^[16] This ever growing waiting list coupled with a nationwide shortage of donor organs has limited transplantation in most regions to high-risk patients in UNOS Status 1A/B, priority levels that only apply to hospitalized patients or those with existing MCS.^[17] As a consequence, ambulatory advanced heart failure patients awaiting transplantation in Status 2 face difficult decisions about if and when to pursue mechanical support. Patients listed in Status 2 on oral therapies must consider the tradeoffs between a major surgical intervention promising a better quality of life coupled with waitlist status upgrade versus ongoing medical therapy. REVIVAL will be the first comprehensive registry of ambulatory advanced heart failure patients to enroll UNOS Status 2 patients for whom the selection of MCS versus ongoing medical therapy prior to transplant is unexplored.

2.0 Specific Objectives

Objective 1: To characterize clinical outcomes, quality of life and functional impairment over two (2) years in a population of ambulatory patients on evidence-based therapy with advanced chronic systolic heart failure who may benefit from VAD therapy

- Characterize ambulatory patients with advanced heart failure at study entry, including measures of functional capacity and (baseline peak VO₂ and serial 6 minute walk test distance), frailty, biomarkers, and quality of life, and interest in VAD therapy.
- Characterize clinical outcomes of these heart failure subjects over two (2) years of follow-up, including a) hospitalizations, Mechanical Circulatory Support Device (MCSD) implant, heart transplant, survival without MCSD or transplant; survival without MCSD, transplant or substantially impaired health utility and b) functional capacity and quality of life.
- Develop improved risk prediction tools for use in this spectrum of advanced ambulatory chronic systolic heart failure.
- Determine if a second early assessment (at two months) of clinical information provides prognostic value that is additive to that of an initial assessment alone.
- Investigate the test performance characteristics of existing classification systems to determine: a) consistency of associated clinical characteristics of a given profile within

and between sites; b) performance metrics such as calibration, discrimination and accuracy; and c) prognostic ability with respect to clinical outcomes over time.

Objective 2: To evaluate the relationship between heart failure subject's modeled prognosis, self assessed prognosis, preferences for end of life care and thresholds for considering VAD implant.

Objective 3: To evaluate caregiver burden associated with heart failure subject's measures of heart failure severity, quality of life, functional limitations and with preferences for care and thresholds for considering device implant.

- Caregiver burden will be assessed at baseline B and again at 6 months, 1 year, 18 months and 2 years to explore its global trajectory, and as a function of each subject's heart failure severity, quality of life and functional limitations, and the caregiver's health status.
- Patient preferences for care and thresholds for considering device implant will be assessed as a function of caregiver burden.
- To describe the trajectory of caregiver burden for caregivers of heart failure subjects before and after transition to VAD therapy or heart transplant.

Objective 4: To determine health-associated costs for heart failure subjects in the registry.

Objective 5: To provide the REVIVE-IT Registry to the INTERMACS study group to be used in comparative analyses of outcomes of patients treated with medical versus VAD therapy.

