3.2 Design

All enrolled heart failure subjects will be followed and assessed for outcomes for two (2) years post enrollment. The following events will be assessed at all but the baseline A visit:

- Hospitalizations
- Stroke
- Mechanical Circulatory Support Device (MCSD)*
- Transplant*
- Death (Cardiovascular related vs. Non-cardiovascular related)*

* Outcomes of death, transplant and implants of a durable VAD will be considered study endpoints with no additional follow-up in REVIVAL. When a study endpoint has been reached, events/outcomes up through the point of the outcome will be reported on the eCRFs.

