4.9 Demographics

Demographic information will be recorded in the study database after consent. In cases where Institutional restrictions limit reporting any component of demographic data, the DCC should be contacted to discuss reporting options. Caregiver contact information (i.e., name, address, phone and email) will be collected to allow for follow-up at the DCC. HIC numbers (if applicable for the subject) and partial social security numbers will be collected from heart failure subjects.

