4.14 Health Status, Patient Perspective and Quality of Life Assessments

This study will use the following health status and QOL assessments:

- a. Heart failure-related QOL (KCCQ)
- b. EuroQoL (EQ-5D)
- c. State-Trait Anxiety Inventory (STAI)
- d. Depression (Personal Health Questionnaire [PHQ-8])
- e. Patient Preferences for end of life care and thresholds for VAD implantation (MEDAMACS VAD Survey)
- f. Caregiver Health QOL (EQ-5D)
- g. Caregiver Oberst Caregiving Burden Scale [OCBS])
- h. Caregiver Health History

QOL assessments will be provided to subjects in English. If a subject does not have proficiency in English, the subject remains eligible for the registry but should not complete the forms.

All heart failure subject QOL assessments and health utility assessment will be administered at all REVIVAL visits. The patient preference questionnaires will also be administered at all visits.

The Caregiver questionnaires will be provided to the heart failure subject's caregiver at the time of the baseline B visit and at each follow up visit. The questionnaires may be mailed to them by the DCC. Detailed instructions for completion of caregiver questionnaires are available in the MOP.

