8.4 Modeling of Other Outcomes

The general approach described in Section 8.3 will be used to evaluate the impact of modeled prognosis, self-assessed prognosis, preferences for end-of-life care on the likelihood that a patients considers a VAD implant [objective 2]; the impact of heart failure severity, quality of life, functional limitations and caregiver health status on caregiver burden [objective 3]; the impact of caregiver burden on patient preferences for care and thresholds for considering device implant [objective 3]; and, the impact of pre- and post-VAD therapy or heart transplant on trajectory of caregiver burden [objective 3].

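### Caregiver burden after durable VAD or transplant is a stated aim and analysis, but the protocol schedules no caregiver assessment after either event

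*Protocol*

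**What the plan says.** The aim appears twice. The last bullet under Objective 3 in Section 2.0 is "To describe the trajectory of caregiver burden for caregivers of heart failure subjects before and after transition to VAD therapy or heart transplant". Section 8.4 lists, among the effects to be modelled, "the impact of pre- and post-VAD therapy or heart transplant on trajectory of caregiver burden [objective 3".

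The stopping rule also appears twice, as a footnote in the Study Summary and in Section 3.2: "Outcomes of death, transplant and implants of a durable VAD will be considered study endpoints with no additional follow-up in REVIVAL". The next sentence limits what is recorded: "When a study endpoint has been reached, events/outcomes up through the point of the outcome will be reported on the eCRFs".

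The caregiver schedule is given in several places:

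- Section 2.0: "Caregiver burden will be assessed at baseline B and again at 6 months, 1 year, 18 months and 2 years".
- Section 4.14: the questionnaires are "provided to the heart failure subject's caregiver at the time of the baseline B visit and at each follow up visit", and "The questionnaires may be mailed to them by the DCC".
- Sections 6.2.3 to 6.2.6 list collection of the caregiver questionnaire as an item of the subject's 6-, 12-, 18- and 24-month visits. Appendix A places it in the subject's visit columns.
- Section 4.9: caregiver contact details "will be collected to allow for follow-up at the DCC".

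Section 13.0, the section on caregivers, deals with consent and withdrawal and sets no follow-up of its own.

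**The concern.** A before-and-after description needs observations on both sides of the event. The event that defines the transition is the same event that ends follow-up, and the caregiver's questionnaires hang on the subject's visits. A site or coordinating centre that follows Section 3.2 literally would stop sending questionnaires at the moment when the post-transition part of the trajectory begins.

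Caregiver burden is self-reported at the time and cannot be rebuilt later from charts. If the matter is left open until analysis, the post-transition term in Section 8.4 may have nothing behind it, and no analysis plan can repair that.

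**Working it through.** The check is mainly one of logic. The passages are set side by side.

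**Step 1. What the aim requires.** At least one caregiver assessment after a durable VAD or transplant (Objective 3, Section 8.4).

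**Step 2. What the schedule offers.** There are five caregiver assessments: baseline B (about two months after consent, Section 6.2.1) and months 6, 12, 18 and 24. All are attached to subject visits.

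**Step 3. Apply the stopping rule.** After a durable VAD or transplant no further subject visit takes place, so no further caregiver assessment is scheduled. Ignoring visit windows, the counts per caregiver are:

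| Transition falls between | Before transition | After, as written | After, if the caregiver continued to month 24 |
|---|---|---|---|
| consent and baseline B | 0 | 0 | not applicable: caregiver not yet consented under Section 6.2.2 |
| baseline B and month 6 | 1 | 0 | 5 − 1 = 4 |
| months 6 and 12 | 2 | 0 | 5 − 2 = 3 |
| months 12 and 18 | 3 | 0 | 5 − 3 = 2 |
| months 18 and 24 | 4 | 0 | 5 − 4 = 1 |

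The third column is 0 in every row, so the result does not depend on how many subjects make the transition.

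**Step 4. Look for an exemption.** Mailing (Section 4.14) and retained contact details (Section 4.9) make continuation feasible. Neither says that questionnaires continue after the subject's endpoint, or when.

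**Step 5. Cross-check with Section 8.2.** The sample-size text takes 30% of 400 = 120 subjects as reaching outcomes such as death or VAD, or dropping out, and leaves 400 − 120 = 280 with year 2 data. The figure reproduces. It treats subjects with a VAD as giving no year 2 data, in line with Section 3.2.

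**Step 6. How many caregivers?** The 120 is not split into death, VAD, transplant and dropout. If the forecast is taken at face value, fewer than 120 subjects would have a durable VAD or transplant, because deaths and dropouts are in the same total. Caregivers may decline (Sections 4.1 and 13.0), so the number of caregivers is smaller still. The protocol supports nothing more exact.

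**The case against.** The strongest reply is that the stopping rule concerns heart failure subjects only. Section 3.2 opens with subjects, the rule is a footnote to the list of subject events, and its second sentence is about events on the case report forms. Caregivers consent separately and may withdraw separately. Section 2.0 gives their assessment times without making them conditional on the subject being free of an endpoint. With mailing and retained contact details, one can read the design as stopping the subject while the caregiver carries on, with the detail in the Manual of Procedures, which Section 4.14 cites and which is not available here.

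That reading is possible and may be what was intended. It means that a reader should not infer that all caregiver follow-up stops, or that no post-transition data will exist: the documents show only that this protocol provides for none. It does not remove the inconsistency. The rule's wording is general, caregivers consent to REVIVAL itself, every operational listing ties the questionnaire to a subject visit, and nothing states the exception that the aim needs.

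Three further inferences would also go too far.

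- The rule covers a durable VAD, not every mechanical support device. A temporary device does not end follow-up.
- Caregivers of subjects who make the transition do not all contribute pre-transition data. A transition before baseline B yields none.
- A headcount based on an assumed transition rate is not supported. For example, 25% of 400 would be 100 of the 120 in Section 8.2, leaving only 20 for all deaths and dropout.

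The reply is also right about scale. This is one descriptive bullet and one modelling clause, and the Study Summary's version of Objective 3 does not include it.

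**Conclusion.** The point holds as an internal inconsistency. Objective 3 and Section 8.4 call for caregiver burden after durable VAD or transplant. Section 3.2, the Study Summary, Section 4.14, Sections 6.2.3 to 6.2.6 and Appendix A together schedule no such assessment. The size is 0 planned post-transition assessments per caregiver, and this needs no assumption about event rates. It rests on reading the stopping rule as it is worded, without an unstated exception for caregivers.

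Only the post-transition part of this sub-aim fails. The overall burden trajectory, its relation to subject severity, quality of life and function, and the link from burden to patient preferences can all proceed, as can the risk modelling and the precision statement in Section 8.2. It should be fixed, but it does not threaten the registry's main purpose.

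**What to change.** Preferred: state in Sections 3.2 and 4.14 that durable VAD or transplant ends the heart failure subject's follow-up only, and that a consented caregiver continues the OCBS and EQ-5D questionnaires, mailed by the coordinating centre, at whichever of months 6, 12, 18 and 24 remain. Mark this in Appendix A. The cost is a protocol amendment, caregiver consent wording with IRB review at up to 25 sites, and the mailings. No subject visits or procedures are added.

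Two limits remain under this option. The subject's severity, quality of life and function would still be unmeasured after transition, so post-transition burden could not be related to them. Late transitions would give only one or two post-transition points, as the table shows.

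Alternative: delete the bullet in Section 2.0 and the matching clause in Section 8.4, and state that caregiver burden is described only up to durable VAD or transplant. This is a wording change, at the price of giving up the sub-aim.
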